6.1.2. Visit 2 (treatment), Day 1-5

The following activities and assessments will be performed on day 1, prior to start of treatment with imlifidase or PE:

- Blood pressure, pulse rate and respiratory frequency, and body temperature
- Baseline samples for DSA, PK, PD, and ADA (IgG) will be collected prior to start of treatment
- P-creatinine
- Urine sample for measurement of albumin/creatinine ratio

Imlifidase arm: Methylprednisolone, antihistamine and antibiotic prophylaxis will be administered before the imlifidase infusion.

PE arm: Methylprednisolone and antibiotic prophylaxis will be administered before the first treatment.

Treatment with antibiotics will continue until IgG levels return to acceptable values as judged by the investigator. Methylprednisolone will be administered according to treatment schedule, see [Section 5.3](#).

The following activities will be performed after the start of treatment:

- Blood pressure and pulse rate will be monitored at 2, 6, 24, 48, 72, and 96 hours
- Respiratory frequency and body temperature will be monitored at 24, 48, 72, and 96 hours
- Safety laboratory tests ([Table 5](#)) will be collected at 24, 48, 72, and 96 hours
- Urine sample for measurement of albumin/creatinine ratio at 24, 48, 72, and 96 hours.
- Imlifidase arm: Samples for PK will be collected at 30 minutes and 1 hour
- Samples for DSA, PK and PD will be collected at 2 and 6 hours
- Samples for DSA, PK, PD and ADA (IgG) will be collected 24 hours after treatment.
- Samples for DSA, PK and PD will be collected at 48, 72, and 96 hours. The 72-hour sample must be taken prior to high dose IVIg is given in the imlifidase arm

Imlifidase arm: High dose IVIg will be given on day 4 (at least 72 hours after the imlifidase infusion). Dose may be given over 2 days as judged by the investigator.

6.1.3. Visit 3, Day 6

The following activities and assessments will be performed:

- Blood pressure, pulse rate and body temperature will be monitored
- Safety laboratory tests (Table 5) will be collected
- Samples for DSA, PK and PD will be collected
- Urine sample for measurement of albumin/creatinine ratio

6.1.4. Visit 4, Day 8

The following activities and assessments will be performed:

- Blood pressure, pulse rate and body temperature will be monitored
- Safety laboratory tests (Table 5) will be collected
- Urine sample for measurement of albumin/creatinine ratio
- Samples for DSA, PK, PD and ADA (IgG) will be collected

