2.4 Randomisation

The 30 patients will be allocated to the treatments by using block randomization. The randomizing will be 2:1 where 20 patients are treated with imlifidase and 10 patients are treated with PE. No stratification is used in this study.

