4.1.1 Data presentation

No formal statistical hypothesis testing will be performed in this study.

The data will be presented descriptive and for some of the endpoints 95% confidence intervals for the treatment difference will be presented.

Numerical data will be presented in summary tables by number of patients, arithmetic mean, median, standard deviation (SD), minimum and maximum.

When numerical data are recorded at different time points, absolute values at each time point and changes from baseline may be presented in the summary tables.

Categorical data will be presented by frequency and percent of patients. Number of events will also be reported where applicable.

Summary tables will in general be presented by treatment group and total across treatment groups unless this is not appropriate for specific tables.

Data will be listed by treatment group, patient and time point (if applicable).

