4.6 Efficacy

4.6.1 Primary efficacy analysis

The primary endpoint is the maximum reduction in DSA at any time point during 5 days following start of treatment. No formal statistical hypothesis will be tested for the primary endpoint. The FAS and PPS set will both be used for the primary endpoint. The primary endpoint will be calculated as part of the ADaM programming.

The DSAs are given as levels of mean fluorescence intensity (MFI) and genetic region of interest. These parameters are used to calculate the reduction in DSA for individual patients in the following steps:

- 1) Determine the DSAs having MFI levels larger than or equal to 1000 at baseline for the considered patient. Calculate DSA_0 as the sum of these MFI levels.
- 2) Calculate DSA_t for each patient as the sum of the MFI levels for the time point t , using the DSAs from step 1.
- 3) The reduction (%) is calculated as $100 \times (DSA_0 - DSA_t) / DSA_0$ for each patient and time point. In the formula DSA_t is the total MFI level at time t .
- 4) The time point with maximum reduction within 5 days is found and chosen for each patient.

- 5) The maximum reduction per patient is a single value as the primary endpoint for the patient.

The difference in reduction between the two treatments will be presented with 95% CI in a table. The confidence interval for the difference in the reduction is found by using an Analysis of variance (ANOVA) model with treatment as fixed effect.

The reduction of DSAs calculated per patient will also be presented in a summary table by treatment and visit and presented in a mean plot by treatment and time point. The maximum reduction per patient will be listed by patient.

If the normality assumption is violated, sensitivity analyses using transformations of the primary endpoint will be performed.

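### The primary ANOVA has treatment as its only term; a prespecified ANCOVA with log pre-dose DSA would be a cheap refinement in 20+10 unstratified patients

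*SAP*

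**What the plan says.** **Endpoint.** SAP 4.6.1 first selects the antibodies that count: "Determine the DSAs having MFI levels larger than or equal to 1000 at baseline for the considered patient". It then says: "Calculate DSA_0 as the sum of these MFI levels". The endpoint is each patient's largest value of 100 × (DSA_0 − DSA_t)/DSA_0 within 5 days. Protocol 12.3.1 gives the same derivation.

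**Model.** "The difference in reduction between the two treatments will be presented with 95% CI in a table". The interval "is found by using an Analysis of variance (ANOVA) model with treatment as fixed effect". Protocol 12.3.1 names no covariate either.

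**Design.** SAP 2.4 plans that "20 patients are treated with imlifidase and 10 patients are treated with PE", in blocks, and adds: "No stratification is used in this study".

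**Other analyses of the primary endpoint.** SAP 4.6.1 allows transformations if normality fails and repeats the analysis in the PPS. SAP 4.6.3 adds nothing further. No planned analysis adjusts for baseline.

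**Availability of the covariate.** Protocol 6.1.2 states: "Baseline samples for DSA, PK, PD, and ADA (IgG) will be collected prior to start of treatment". Since DSA_0 is the denominator of the endpoint, every patient with an evaluable endpoint has it.

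**Purpose.** "No formal statistical hypothesis testing will be performed in this study" (SAP 4.1.1). The quantitative support for the sample size is the expected interval width of about 8 percentage points (Protocol 12.4, SAP 2.2).

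**The concern.** With only 10 controls and no stratification, the arms can easily differ in starting DSA by chance. Dividing by DSA_0 puts patients on a common scale, but it does not make the percentage reduction independent of DSA_0. The denominator carries assay error. The 1000 MFI threshold also admits patients with low starting levels, in whom any residual background signal would limit the percentage that can be reached. If the percentage does depend on starting level, part of an imbalance carries through to the estimated difference, and variation that a covariate could explain stays in the error term.

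This matters because the trial is built on estimation: the width of this one interval is what the documents use to support 20+10. The timing also matters. The study is open-label (SAP 2.3), so a baseline adjustment added after an imbalance has been seen would look data-driven.

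**Working it through.** **Inputs.** n = 20 and 10 (SAP 2.4). The SDs of 6% and 4% are for IgG reduction in two earlier studies (Protocol 12.4, SAP 2.2), and I use their average, 5. The same SD in the PE arm is the protocol's assumption. The within-arm correlation rho between log(DSA_0) and maximum percentage reduction is not in the documents. It is assumed and shown over a range.

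**1. The plan's own width.** Full width = 2 × t(0.975, 28) × SD × √(1/20 + 1/10) = 2 × 2.048 × 5 × 0.387 = 7.93 points. The root-mean-square SD of 5.10 gives 8.09. The stated figure of about 8 is reproduced, and it is the width of the treatment-only model.

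**2. Chance imbalance.** The baseline difference in SD units has standard error √(1/20 + 1/10) = 0.387. For 0.5 SD, z = 0.5/0.387 = 1.29 and the two-sided probability is 0.197. For 0.75 SD it is 0.053.

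**3. Shift in the unadjusted estimate.** Shift = rho × imbalance × SD.
- At exactly 0.5 SD: 0.3 × 0.5 × 5 = 0.75 points; 0.5 × 0.5 × 5 = 1.25 points.
- Averaged over the 20% of trials beyond 0.5 SD, the mean imbalance is 0.387 × 0.1734/0.0984 = 0.68 SD (normal density over tail area at 1.29). The shift is then 0.3 × 0.68 × 5 = 1.02 points, or 0.5 × 0.68 × 5 = 1.70 points.

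The half-width of the interval is about 4 points.

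**4. Width with log(DSA_0) added, common slope.** Approximate ratio of widths = √[(1 − rho²) × (1 + 1/26)] × t(0.975, 27)/t(0.975, 28), with t values 2.0518 and 2.0484. At rho = 0 this is √1.0385 × 1.0017 = 1.02. It equals 1 at rho = 0.20. Simulation (40,000 trials of 20+10, normal data, SD 5) agrees:

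| rho (assumed) | ANOVA mean width | ANCOVA mean width | Change |
|---|---|---|---|
| 0 | 7.86 | 8.02 | +2% |
| 0.2 | 7.86 | 7.86 | none |
| 0.3 | 7.86 | 7.65 | −3% |
| 0.4 | 7.86 | 7.35 | −6.5% |
| 0.5 | 7.86 | 6.94 | −12% |

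The simulated ANOVA mean is slightly below 7.93 because the estimated SD averages a little under 5.

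**5. Slope not common.** With no slope in the imlifidase arm and rho 0.5 in the PE arm only, the mean widths are 7.86 (ANOVA) and 7.91 (ANCOVA). With PE-arm rho 0.3 they are 7.86 and 7.98. With opposite slopes (+0.3 and −0.3), the SD of the adjusted estimate is about 2.00, against 1.93 unadjusted.

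**6. Validity of the planned interval.** With equal variances, simulated coverage of the treatment-only ANOVA is 95%. If the PE-arm SD were 15 and the imlifidase SD 5 (assumed), coverage falls to about 85 to 86% for the ANOVA and about 86 to 87% for the ANCOVA.

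**The case against.** The strongest reply has four parts.

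- **The endpoint already uses baseline.** It is a percentage of each patient's own DSA_0. A reader might infer from the bare model that starting DSA is ignored altogether. The documents do not support that: it is absent from the model but present in the endpoint. What remains is that scaling does not ensure independence from baseline.
- **The precision gain is unproven.** A reader might infer that the plan is certainly giving up precision. That needs |rho| above about 0.2 and a roughly common slope, and the documents report no correlation. Protocol 12.4 quotes IgG reductions of 90% and 93% with imlifidase. If DSA behaves similarly, the 20-patient arm sits near the ceiling and may show little slope. Step 5 shows that the gain then disappears. This stands, and the gain can be claimed only conditionally.
- **The unadjusted interval is valid.** Over repeated randomisation it already allows for chance imbalance if variances are equal, and a shift of about one point is small beside a width of 8. This also stands. It does not help in the one trial actually run if that trial happens to be imbalanced.
- **The study is exploratory, and readers can see the data.** DSA is listed by patient and time point, with individual and mean plots (SAP 4.6.2 and section 8), so an imbalance would be visible. An adjustment made after seeing it would carry less weight than a prespecified one.

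Unequal variance between arms could matter more for the width and coverage than baseline adjustment does. It is a separate matter that a covariate does not solve.

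**Conclusion.** The point holds as a missed refinement. The primary model has treatment as its only term, randomisation is unstratified, and no planned analysis adjusts for starting DSA, although DSA_0 is available for every evaluable patient. The exposure is about a 20% chance of an imbalance above 0.5 SD. At 0.5 SD, the estimate would shift by 0.75 points (rho 0.3) or 1.25 points (rho 0.5).

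These sizes rest on the planning SD of 5, which comes from IgG and not DSA, on similar variability in the PE arm, and on assumed correlations. The effect of adjustment on width runs from about 2% wider to about 12% narrower for a common rho between 0 and 0.5.

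A reader might go further and infer that the planned analysis is biased or invalid. The documents do not support that: under equal variances the ANOVA is unbiased over repeated randomisation and its interval has the stated coverage.

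**What to change.** Before database lock, amend SAP 4.6.1 to prespecify an ANCOVA of maximum percentage DSA reduction with treatment as factor and log(DSA_0) as covariate. DSA_0 is the baseline sum already defined in step 1 of that section. Report the adjusted difference with its 95% CI, and present the unadjusted ANOVA alongside in tables 14.2.1 and 14.2.2.

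This needs one model term, one degree of freedom and no new data. The interval may be slightly wider (about 2%) if starting DSA turns out to be unrelated to the percentage reduction. Label: cheap improvement. The change does not deal with unequal variances between the arms, which need their own provision.

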12.4. Determination of Sample Size

Due to the exploratory nature of the study, there is no formal statistical hypothesis. The difference between treatments for the reduction of DSA will however be presented with 95% confidence interval. A sample size of 20 implifidase and 10 PE subjects is proposed.

In two previous implifidase studies, 14-HMedIdeS-04 and 15-HMedIdeS-06, the IgG reduction for 5 days was 90% and 93% respectively. The corresponding standard deviations are 6% and 4% respectively. Assuming a similar variability in the PE treatment arm, the expected width of the 95% CI for the difference in DSA reduction will be around 8% point. This supports that 20+10 patients are appropriate. Also, the sample size is in line with experience from previous similar Phase II studies with other compounds to obtain adequate safety, tolerability and PK data to achieve the objectives of the study.

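### The non-normality fallback for the primary interval names no trigger, transformation or boundary rule, and nothing covers unequal variances at 20 v 10

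*SAP*

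**What the plan says.** SAP 4.6.1 computes R = 100 × (DSA_0 − DSA_t)/DSA_0 at each time point and keeps the largest value within 5 days: "The maximum reduction per patient is a single value as the primary endpoint for the patient". The interval is then specified: "The confidence interval for the difference in the reduction is found by using an Analysis of variance (ANOVA) model with treatment as fixed effect". With two arms and no covariate, this is the equal-variance t interval with 28 degrees of freedom. The only provision for failed assumptions is: "If the normality assumption is violated, sensitivity analyses using transformations of the primary endpoint will be performed".

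Neither document names the transformation, the criterion for a violation, the handling of values at or beyond a boundary, or the route back to percentage points. Protocol 12.3.1 adds nothing on this. SAP 2.3 describes the trial as fully unblinded.

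Protocol 12.4 gives the only quantitative guide to the distribution. It uses total IgG in two earlier imlifidase studies as a stand-in for DSA: "the IgG reduction for 5 days was 90% and 93% respectively", and "The corresponding standard deviations are 6% and 4% respectively". For the control arm it only assumes similar variability; no PE mean or SD is given.

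**The concern.** R is capped at 100 but can be zero or negative if no post-dose value falls below baseline. Means of 90 and 93 with SDs of 6 and 4 lie (100 − 90)/6 = 1.7 and (100 − 93)/4 = 1.75 SDs below the cap, so a left tail in the imlifidase arm is foreseeable. Log and square root are for right-skewed data. Applied to R they lengthen a left tail, and log R does not exist at R ≤ 0. An analyst could therefore follow the SAP and report a worse interval, having chosen both trigger and transformation with arm-level data in view.

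Non-normality is also not the only assumption at risk. The arm near the cap has little room to vary, while the PE arm may vary more and has half the patients. A pooled variance then makes the interval too narrow, and the fallback sentence does not address this.

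**Working it through.** **1. The plan's own figure.** Width = 2 × t(0.975, 28) × SD × √(1/20 + 1/10), with t = 2.048. This gives 6.35 at SD 4, 7.93 at SD 5 and 9.52 at SD 6. The stated width of around 8 percentage points is reproduced at SD 5, provided both arms share that SD.

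**2. Skewness of R in the imlifidase arm.** The documents give no shape, so two were assumed and simulated. *Beta*: mean 90, SD 6. *Lognormal residual*: 100 − R has median 7 and log SD 0.6. Its SD is 7 × e^0.18 × √(e^0.36 − 1) = 5.5, within the protocol's 4 to 6.

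| Scale | Beta | Lognormal residual |
|---|---|---|
| R | -1.03 | -2.2 |
| √R | -1.15 | -2.7 |
| log R | -1.29 | -3.5 |
| log(100 − R) | -0.80 | 0.0 |
| arcsine-√(R/100) | -0.31 | not run |

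At mean 93, SD 4 the beta model shows the same pattern. The log R value in the lognormal model varies with the draws (-3.8 in a longer run).

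**3. Values with no transform.** Log R fails at R ≤ 0, square root at R < 0, and log(100 − R) at R = 100 (summed MFI of zero). How often R ≤ 0 occurs depends on the PE arm, which must be assumed. For a normal PE arm, the chance of at least one such value among 10 patients is 1.3% at mean 60, SD 20; 21% at 40, 20; and 71% at 30, 25. With lognormal PE residuals (median 40% to 60%, log SD 0.4 to 0.5), 10% to 81% of simulated 20+10 trials contain one.

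**4. Unequal variances.** Take imlifidase SD 5 and PE SD 15 (assumed).
- True variance of the difference: 25/20 + 225/10 = 23.75, SE 4.87.
- Pooled variance: (19 × 25 + 9 × 225)/28 = 89.3. Times 0.15 this is 13.4, SE 3.66.
- The ANOVA SE is therefore 3.66/4.87 = 0.75 of the correct size.

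Simulated coverage of the nominal 95% interval on R, 20 v 10, beta model, imlifidase mean 91.5 and SD 5, PE mean 60 (assumed):

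| PE SD | Pooled: coverage (mean width) | Welch: coverage (mean width) |
|---|---|---|
| 5 | 94.7% (7.8) | 94.9% (8.0) |
| 10 | 88.5% (11.0) | 94.6% (14.4) |
| 15 | 85.3% (14.8) | 94.8% (21.3) |
| 20 | 83.5% (18.8) | 94.5% (28.2) |

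With lognormal residuals (imlifidase median 7%, log SD 0.6; PE median 50%, log SD 0.4), the pooled interval covered 82.5% and Welch 93.2%.

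**5. Transformed scales, each for its own target.** In the beta model with PE SD 10, 15 and 20, the pooled interval on log R covered 84.9%, 81.8% and 80.2%, below raw R. On log(100 − R) it covered 98.2%, 97.3% and 95.4%. In the lognormal setting of step 4, log of the residual fraction covered 97.4%.

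**The case against.** The strongest reply is that the SAP names no transformation, so it cannot be faulted for a bad one. A reader might infer that the fallback necessarily worsens the skew and cannot rescue the interval. The documents do not support that: log(1 − R/100) is itself a transformation of the primary endpoint, the SAP permits it, and step 5 shows that it works. This stands. The defect is that nothing steers the analyst to a helpful choice.

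A reader might also infer that undefined values are likely. R is a maximum over at least six post-dose samples (2, 6, 24, 48, 72 and 96 hours), so R ≤ 0 needs every one at or above baseline. An inert treatment with exchangeable assay noise would give 1/7 = 14% of patients. The 81% figure in step 3 implies about 15% of PE patients, which is no better than inert. It is an extreme, and no PE figure exists to narrow the range.

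Nor would the primary interval be lost. The transformed analysis is a sensitivity analysis. The percentage-point ANOVA interval is reported regardless for FAS and PPS, no hypothesis is tested, and medians, ranges and individual values are shown. This stands too, and limits the point to how far that interval can be trusted.

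Finally, at SDs of 4 to 6 the damage from log or square root is modest in the beta model (-1.03 to -1.29 or -1.15). Much larger skewness needs imlifidase SDs of 10 to 12, which conflict with protocol 12.4.

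**Conclusion.** The point holds as one of under-specification, and it is worth fixing. The primary interval has a single, conditional, open-ended safeguard. Some choices that comply help and others harm, and the larger threat in these simulations, unequal variance with the smaller arm the more variable, has no safeguard. Coverage of the planned interval is about 82% to 88% under the assumed PE spreads, but close to 95% if the PE SD really matches imlifidase.

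These figures rest on assumed beta or lognormal shapes, assumed PE means and SDs, and IgG standing in for DSA, a substitution that protocol 12.4 itself makes. That the sentence is unspecified, and that log R is undefined at R ≤ 0, needs no assumption.

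**What to change.** Replace the conditional sentence in SAP 4.6.1 with two supportive analyses that are reported whatever the data look like:

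- (a) The same treatment-only model on log(minimum DSA_t/DSA_0), which equals log(1 − R/100), back-transformed to a ratio of geometric mean residual DSA with 95% CI. State an MFI floor before analysis, and whether it applies to each antibody or to the sum. This removes the undefined case at R = 100; R ≤ 0 causes no difficulty on this scale.
- (b) A Welch (unequal-variance) 95% CI for the difference in mean maximum reduction, in percentage points.

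A Hodges-Lehmann interval is not a good substitute for (b). It assumes a location shift, and it covered only about 87% to 90% of its own target in the lognormal-residual settings tried, which included imlifidase SDs above the protocol's range. Welch is not perfect under strong skew either (about 91% to 94% there), but it is closer to nominal.

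The cost is a few lines of standard code and one table, with no new data. The downsides are that a floor must be chosen (the documents give no assay background), that (a) is not in percentage points, and that the Welch interval may be wider, for example 21 v 15 points at an assumed PE SD of 15.

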4.6.2 Secondary efficacy analyses

DSA levels up to 180 days after treatment

DSAs will be measured using SAB-HLA assay and a functional assay e.g. C1q or C3d assay. A summary table for the C1q assay will be generated for the sum of MFI levels for DSAs from step 1 for primary endpoint (see Section 4.6.1) by treatment and time point. MFI levels will be listed per patient and time point. Spaghetti plots will show the DSA level versus time for each patient. A mean plot by treatment and time point will be presented.

A list with all DSA by patient and time point will be presented.

HLA-antibodies levels up to 180 days after treatment

Patient listings of MFI values for all HLAs will be presented.

Kidney function change from baseline

The kidney function will be evaluated by the parameters eGFR, P-creatinine and albumin/creatinine ratio in urine. The laboratory parameters will be summarised as part of the safety data tabulation.

The eGFR will be calculated as a part of ADaM programming, using the Modification of Diet in Renal Disease Study (MDRD) equation (2):

$$\text{eGFR (mL/min/1.73 m}^2\text{)} = 175 \times (\text{Cr})^{-1.154} \times (\text{Age})^{-0.203} \times (0.742 \text{ if female}) \times (1.212 \text{ if African American}),$$

where Cr stands for creatinine value and Age are measured in years from birth to screening visit. This formula assumes that Cr is given in the mg/dL unit.

Proportion of patients with graft loss at day 180

The number of patients with graft loss at day 180 will be handled as a binary variable. Graft loss is defined as permanent return to dialysis for at least 6 weeks, re-transplantation, or transplantectomy. The endpoint is a success if the patients have absence of graft loss at day 180. The proportion of patients, which satisfy the success criterium, will be summarized by treatment and listed by patient. The FAS set will be applied.

Signs of transplant glomerulopathy 180 days post treatment

Possible transplant glomerulopathy 180 days post treatment will be handled as a binary variable. The endpoint is a success if the patients have no possible transplant glomerulopathy 180 days post treatment. The proportion of patients, which satisfy the success criterium, will be tabulated by treatment. A list will also be created by patient. The FAS set will be applied.

Change from baseline in histopathology per Banff Criteria at 29 and 180 days

Kidney biopsies will be assessed according to the Banff (2017 or later version) criteria pre-dose and at day 29 and 180. The biopsy data are measured as scores. The scores will be presented by time point in

a summary table. The change from baseline will be summarised by treatment, Banff lesion score and time point.

The overall interpretations for the biopsies will be presented in a summary table by time point. Shift tables will also be presented for overall interpretation from the biopsies. The possible categories for the overall interpretation are: Active AMR, Chronic Active AMR, CMR, Borderline CMR and No rejection. Possible combinations for the overall interpretation are: Active AMR + CMR, Active AMR + Borderline CMR, Chronic Active AMR + CMR and Chronic Active AMR + Borderline CMR.

A list will also be presented by patient where the scores and diagnosis are presented.

Change from baseline in mRNA levels in kidney biopsies evaluated by [REDACTED] at 29 and 180 days from baseline

[REDACTED] data will be presented in a summary table and in a list for day 29 and day 180. The [REDACTED] data is also given as score. The change from baseline will also be presented in a summary table. If baseline data is not available for [REDACTED], only the values on day 29 and 180 will be presented.

Number of sessions with PE for 180 days

The number of PE and immunoabsorption (IA) sessions within 180 days will be summarized by treatment and listed by patient. In addition, the number of PE and IA sessions after start of IVIg administration and up to 180 days after start of study treatment will be summarized by treatment. The FAS set will be applied.

Total serum IgG over time

The FAS set will be applied when analysing total serum IgG.

The IgG levels in serum will be analyzed centrally by a validated ECL based immunoassay using the Meso Scale Diagnostic technology. The total serum IgG levels will be summarized by time point. Total serum IgG levels will also be presented by mean and spaghetti plots. Finally, data will be listed by patient.

In addition, the reduction of total serum IgG levels will be analyzed as a binary endpoint. The binary endpoint is defined as a success, if the minimum IgG value at any time point during the 5 days following the start of treatment is less than 5% of baseline for the patient. The proportion of patients, which satisfy the success criterium, will be presented in a summary table by treatment. The difference in proportion between the two treatments will be presented with a 95% CI in a summary table. The 95% CI for the difference between the two treatments will be based on exact Confidence Limits. In addition, the proportion of patients which satisfy the success criterium will be presented by treatment and time point.

The composition of IgG-fragments will be analyzed centrally using SDS-PAGE. Each sample will be assigned a score depending on the observed composition of fragments as follows:

- 0=no intact IgG, scIgG or F(ab')₂
- 1=only F(ab')₂
- 2=mix of scIgG and F(ab')₂
- 3=only scIgG
- 4=mix of intact IgG and scIgG
- 5=only intact IgG

SDS-PAGE scores will be summarized by time point.

Presence of intact IgG on SDS-PAGE until start of IVIg treatment

The endpoint is a success for a patient if no detectable intact IgG is found by the SDS-PAGE assay for at least one time point between the start of study medication (imlifidase) treatment and start of administration of IVIg. No detectable intact IgG is defined as SDS-PAGE scores 0, 1, 2 or 3. The

proportion of patients, who reached the success criterium, will be summarized in a table using the PKS set.

Number of patients with resolution of AMR at day 180

The number of patients with resolution of AMR at day 180 will be handled as a binary variable. Resolution is defined as “Active AMR” or “Chronic active AMR” not being selected from the biopsy protocol.

The endpoint is a success if the patients have resolution of AMR at day 180. The proportion of patients, which satisfy the success criterium, will be tabulated by treatment. A list will be created by patient. The FAS set will be applied.

Patient survival at day 180

The patient survival on day 180 will be handled as a binary variable.

The endpoint is a success if the patients have survived on day 180. The proportion of patients, which satisfy the success criterium, will be summarized and listed by patient. The FAS set will be applied.

Pharmacokinetic

The Pharmacokinetic (PK) characteristics of imlifidase will be analyzed using the PKS. Imlifidase concentration in serum will be analyzed centrally using a validated electrochemiluminescence (ECL) based immunoassay (Meso Scale Diagnostic) technology. Full details of the analytical method used, and the analysis results will be detailed in a separate bioanalysis report.

The PK parameters will be calculated by non-compartmental analysis (NCA) and/or compartmental analysis using the software WinNonlin (Pharsight Corporation, USA). Actual sampling time points relative to dosing will be used for the calculation and on the individual plots of plasma concentration versus time. Plasma concentration values missing (e.g., no blood sample collected, or no value obtained at analysis) will be excluded from the calculations. Values below lower limit of quantification (LLQ) will be represented by ‘0’ (zero) in the descriptive statistics and as LLQ/2 in the plots. No formal analysis of outliers is planned.

PK parameters will be estimated based on measurements of the plasma concentration-time data of imlifidase, and the following parameters will be estimated, if possible, but not limited to: AUC, C_{max} , t_{max} , $t_{1/2}$, CL, and V_z .

Imlifidase concentrations will be listed by patient, visit and time point. Imlifidase concentrations will also be presented in a summary table by time point. PK parameters including but not limited to AUC, C_{max} , t_{max} , $t_{1/2}$, CL, and V_z , will be listed by patient and visit, by treatment arm, and summarized with number of measurements, arithmetic mean, standard deviation, percentage coefficient of variation (%CV) (arithmetic), median, minimum, maximum, geometric mean, and %CV (geometric mean). For $t_{1/2}$, the harmonic mean, median, minimum, and maximum will be presented, and for t_{max} only the median, minimum, and maximum will be displayed.

Further, the PK concentrations will be presented graphically as mean profile plots and as spaghetti (individual lines) plots. Semi-log format with log10 on the y-axis and a linear time on the x-axis will be presented in the plots. Linear-linear plots may also be presented.

